## 5.3 Missing Data

General linear models will be used to allow inclusion of all data in the analysis without the need to use ad hoc imputation procedures such as last observation carried forward. This maximum-likelihood based approach is fully efficient (assuming that covariates are completely observed).

### Sensitivity Analyses

To assess for any potential bias due to attrition, we will examine differences between patients with complete data and those lost to follow-up based on all available covariates at baseline. A sensitivity analysis using multiple imputation under assumptions of "missing not at random" will be used to examine potential bias due to informative drop-out.

## 5.4 Harms

### Adverse Event (AE)

An adverse event is any untoward medical occurrence in a research participant administered an investigational product and which does not necessarily have a causal relationship with the study product. An AE can therefore be any unfavourable and unintended sign (including an abnormal lab finding, for example), symptom, or disease temporally associated with the use of an investigational product, whether or not considered related to the investigational product.

The following definitions are to be used for guidance for determining severity of adverse events:

- Mild – An awareness of symptoms but easily tolerated
- Moderate – Symptoms interfere with normal daily activities
- Severe – Symptoms are incapacitating with inability to perform daily activities

### Adverse Drug Reaction (ADR)

All noxious and unintended responses to an investigational product related to any dose should be considered adverse drug reactions. The phrase "responses to an investigational product" means that a causal relationship between the investigational product and an adverse event is at least a reasonable possibility (i.e. the relationship cannot be ruled out).

### Serious Adverse Event (SAE) or Reaction

An SAE is any untoward medical occurrence that:

- Results in death
- Is life-threatening
- Requires inpatient hospitalization or prolongation of existing hospitalization
- Results in persistent or significant disability/incapacity
- Results in congenital anomaly/birth defect
- Based on medical judgement, is an important medical event that may require medical intervention to prevent one of the outcomes listed above.

---

 RJA Little. 1995. Modeling the drop-out mechanism in repeated-measures studies. Journal of the American Statistical Association 90(431): 1112-1121.

**Note:** The term “life-threatening” in the definition of “serious” refers to an event in when the participant was at risk of death at the time of the event; it does not refer to an event which hypothetically might have caused death if it were more severe.

#### Unexpected Adverse Drug Reaction

UADR is an adverse reaction, the nature or severity of which is not consistent with the applicable product information (i.e. the Investigator’s Brochure for an unapproved investigational product). Reports which add significant information on specificity or severity of a known, already documented serious ADR constitute unexpected events. For example, an event more specific or more severe than described in the Investigator’s Brochure would be considered “unexpected”.

#### Expected Adverse Events in This Patient Population

The following is a list of expected adverse events in the PAH population which should be used for guidance when determining expectedness of adverse events for the trial:

- Right heart failure
  - Peripheral edema
  - Pleural or pericardial effusions
  - SOB/dyspnea
  - Liver dysfunction
- Chest pain, angina
- Syncope
- Hypotension
- Supraventricular arrhythmias, atrial fibrillation
- Side effects of concomitant PAH therapies
  - Prostanoids and prostaglandin receptor agonists: hypotension, headache, flushing, nausea, vomiting, diarrhea, jaw pain, thrombocytopenia, musculoskeletal pain
  - ERAs: peripheral edema, elevated LFTs, anemia, headache, nasal congestion
  - PDE5 inhibitors and sGC stimulators: Headache, flushing, hypotension, priapism, GERD, visual changes
  - High dose Lasix: Hearing loss
  - Anticoagulants: Bleeding, bruising
- Hypoxemia, intrapulmonary shunting
- Right to Left shunting with rising right sided pressures
- Renal dysfunction
- Pulmonary Edema (in the context of a very severe reduction in cardiac output)

#### Expected Adverse Events during Apheresis

Guidance for determining expectedness of adverse events that occur during apheresis can be found in the Apheresis Risks section of the Informed Consent Form.

#### Determination of Adverse Event Relationship to Study Product

For study participants having received at least one dose of the study product, guidance for determining the relationship and expectedness of adverse events can be found in Section 5 of the Investigator’s Brochure.

### Recording and Reporting Adverse Events

At each contact with the patient, the investigator will seek information on adverse events by specific questioning, and as indicated, by examination. All adverse events occurring during the study period will be recorded. Information on non-serious adverse events should be recorded in the case report form with indication of the possibility of relationship to the cell delivery procedure or the delivered cells. Causality of all adverse events must be determined by the Principal Investigator or a sub-investigator. **A serious adverse event form must be completed for all serious events and sent to Allphase Clinical Research Inc. by email to [[contact]](mailto:[contact]) within 24 hours of the investigator's knowledge of the event.**

At the time of the initial SAE report, the following must be recorded on the SAE Report Form: participant unique study number, randomization number, description of the event, date of onset of event, any treatment given for the event, whether investigative treatment was discontinued prematurely, the reason why the event was classified as serious, and the investigator's assessment of the association between the event and the study product/procedure. The Principal Investigator must also provide prompt reporting of any follow-up information on each serious adverse event. This should include copies of the completed supplemental serious adverse event forms and any other diagnostic information that would assist in the understanding of the event.

In addition, the Principal Investigator is required to report all adverse events to the REB in accordance with local reporting requirements. The following AEs do not normally require reporting to the REB:

- Serious adverse events that are considered expected
- Serious adverse events that are considered not related to the investigational product or research procedures, whether the event is expected or not
- Non-serious adverse events, whether expected or not.

Northern Therapeutics, Inc. is responsible for reporting *Unanticipated Problems (serious and unexpected events which are deemed related or possibly related)* to Health Canada. These events must be reported within **15 days** after becoming aware of the information if the event is neither fatal nor life threatening. However, if an event is fatal or life threatening, the information should be reported within **7 days** after becoming aware of the information. A complete report which includes an assessment of the importance and implication of any findings should be submitted within **8 days** of the initial report.

### Analysis of Safety

Safety endpoints related to the tolerability and safety of injection of the study product in patients with severe PAH will be divided into early and late endpoints.

Early (within 1 hour of each study product administration):

- Clinical evidence of allergic or other immune reaction that in the opinion of the investigator is possibly related to the cell product injection
- Evidence of pulmonary or systemic embolization
- Symptomatic hypotension
- A clinically significant drop in O2 saturation.

Late (within 1 month [visits 0-2 and 6-8] or 3 months [visits 3 and 9] of study product delivery):

- Evidence of significant immune activation (i.e. increases in ESR, CRP)
- Evidence of new and more than mild right to left shunting (i.e. greater than grade 2 shunting) by semi-quantitative analysis on agitated saline contrast echocardiography; or new evidence of rapid appearance of contrast in the left atrium.

A safety analysis is planned after the first twelve participants complete primary endpoint data collection at the 6-month follow-up visit. Safety data will be sorted by treatment arms (blinded) to determine the distribution of potential safety concerns and be provided to the DSMB for review. The unblinded treatment allocation will be available from the statistician should the DSMB determine that a safety concern exists that necessitates unblinding.

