Potential immediate risks of this cell therapy include adverse events related to possible pulmonary or systemic embolization, and allergic or other immune reactions (see Section 11.9 – Analysis of Safety). To ensure optimal safety following administration of the study product, vital signs and O_2 saturation will be closely monitored for a minimum of 1 hour post study product delivery, with approval required by a study investigator prior to discharge from the clinic. While the possibility of immune reactions has been minimized by using an autologous cell product, standard clinical therapies including antihistamines and corticosteroids will be available for treatment of symptoms should the need arise.

7.10. Rescheduling Missed Study Treatment Visits:

In the event that a study participant is unable to attend a scheduled treatment visit, or the study product does not arrive at the study site on time for delivery, every effort will be made to reschedule the treatment visit so that a new study product can be manufactured and administered within 2 weeks of the cancelled visit.

In cases where the study product administration cannot be performed within 2 weeks of the originally scheduled visit date, the dose for the study visit will be considered "missed" and the next study visit will take place according to the protocol visit schedule.

8. Post Treatment Phase Conversion to a Long-Term Follow-up Registry

Changing the study to a long-term follow-up registry following completion of the 12-month treatment phase of the trial will permit participants to enroll into other trials following data collection at the 12-month visit post first administration of study product. The registry will consist of a yearly telephone contact (± 14 days) to capture serious adverse event data over a 10 year period.

9. Blinding/Unblinding

9.1. Emergency Unblinding:

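### Embolization, allergic or immune reaction, hypotension and desaturation are safety endpoints only in the first hour after injection, and no final by-arm adverse event analysis is planned to pick up later ones

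*SAP*

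**What the plan says.** The Analysis of Safety text in SAP 5.4 states that the safety endpoints "will be divided into early and late endpoints". Protocol 11.9 carries the same two lists.

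- The early list is headed "Early (within 1 hour of each study product administration". It has four items. The first is "Clinical evidence of allergic or other immune reaction that in the opinion of the investigator is possibly related to the cell product injection". The others are embolization in the lungs or the systemic circulation, hypotension with symptoms, and a clinically significant fall in oxygen saturation.
- The late list covers 1 month after the injections at Months 0–2 and 6–8, and 3 months after those at Months 3 and 9. It has two items. One is "Evidence of significant immune activation (i.e. increases in ESR, CRP", where the bracket closes the definition on those two markers. The other is new right-to-left shunting above grade 2 on contrast echocardiography, or newly rapid contrast in the left atrium.

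The rest of SAP 5.4 defines AEs, ADRs and SAEs, lists the expected events, and sets recording and reporting rules. All AEs in the study period are recorded. One safety review is planned, after twelve participants reach Month 6, with safety data sorted by arm for the DSMB.

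**The concern.** The four clinical events stop counting as endpoints 1 hour after injection, which is also the earliest time at which a participant may leave the clinic (Protocol 7.1 and Appendix H). The late list starts from the same delivery and runs for months, but names none of the four. An embolization on day 2 therefore falls outside the early window and inside a late window that does not list it.

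This would matter less if the plan also compared all AEs and SAEs between arms at the end of the trial. It does not say that it will. Efficacy and safety together are the trial's stated objective, and embolization and immune reaction are the risks that Protocol 7.9 attaches to this product. A final report could follow the SAP exactly and still be silent on either event when it occurs after discharge.

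**Working it through.** The plan states no figure on this point, so the check is to trace events through the text and then add up the windows.

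**Step 1. What each list counts (SAP 5.4, Protocol 11.9).**

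| Event | Within 1 hour | After 1 hour, inside the late window |
|---|---|---|
| Pulmonary or systemic embolization | Endpoint | Not listed |
| Allergic or immune reaction, possibly related | Endpoint | Not listed as a clinical event; may register if ESR or CRP rises |
| Symptomatic hypotension | Endpoint | Not listed |
| Clinically significant desaturation | Endpoint | Not listed; the shunting item covers only desaturation that goes with new shunting |

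Neither list has wording that would admit further items.

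**Step 2. Is a late event analysed anywhere else?** Take an embolization on day 2.

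- *AE and SAE recording* (Protocol 10.8, SAP 5.4): captured, and sent to the CRO within 24 hours if serious. No final tabulation or comparison by arm is specified.
- *Regulatory and ethics reporting*: sponsor reporting to Health Canada covers serious, unexpected events judged related or possibly related. Expected SAEs do not normally go to the REB. Hypotension and hypoxemia are on the expected list, so later cases of these two are the least likely to surface by this route.
- *Hold criteria* (Protocol 9.3, SAP 2.5): no 1-hour limit, but they turn on death, a major cardiovascular event or a life-threatening response, with a definite relation to the product as judged by the DSMB.
- *Clinical worsening* (Protocol 11.8, SAP 5.1): reached through death, hospitalization attributed to disease progression, a 15% or greater fall in 6MWD, or a worse WHO class. This is an efficacy outcome and does not identify embolization.
- *Twelve-participant review*: covers safety data, a term that is not defined. A day-2 event may be included, but nothing says that it must be.

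No route produces a planned between-arm result for these events after the first hour.

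**Step 3. What the late windows cover.** Per course there are three injections with a 1-month window and one with a 3-month window: 3 × 1 + 1 × 3 = 6 months. Over two courses, 2 × 6 = 12 months. On the nominal schedule the late windows therefore run without a gap from Month 0 to Month 12, and the Course 1 windows end at Month 6, when the first Course 2 injection is due. Adding events to the late list needs no new window, and Course 1 can be analysed on its own.

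**Step 4. Which comparison is clean.** In Course 1, Arms 2 and 3 receive cells and Arm 1 receives placebo: 15 + 15 = 30 against 15 participants as randomized. In Course 2, Arm 1 receives cells for the first time, Arm 3 receives a second course, and Arm 2 receives placebo after 4 × 20 = 80 million cells. No arm in Course 2 is both on placebo and unexposed, so pooling Course 2 as cells against placebo would credit any late cell effect in Arm 2 to placebo.

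**The case against.** The best defence is that the early list is meant to be acute. Protocol 7.9 says "Potential immediate risks of this cell therapy include adverse events related to possible pulmonary or systemic embolization, and allergic or other immune reactions" and points to Section 11.9. The endpoints are framed around the safety of the injection itself. The phase 1 study judged safety by hemodynamics before and 30 minutes after delivery, and a 1-hour window matches the post-dose monitoring. Later events are recorded, their causality is assessed, and they can reach the DSMB.

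Much of this stands. A separate 1-hour list is a legitimate choice and should stay. It explains the acute list, but it does not explain why the same events have no planned analysis afterwards. Phase 1 cannot show that later events are negligible. It had 7 patients and used electroporated plasmid DNA with central delivery under intensive-care monitoring. This trial uses minicircle DNA with a different transfection method and up to eight peripheral outpatient injections of cells. The protocol's own rationale is that cells lodge in the pre-capillary arterioles and that transgene expression is prolonged.

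Some stronger readings are tempting but lack support:

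- *All four events are named product risks.* Protocol 7.9 names two, embolization and immune reaction, and calls them immediate. Hypotension and hypoxemia appear as expected events in PAH.
- *Late events are lost, or no late immune endpoint is possible.* Neither follows. The gap is in endpoint definition and planned analysis, not in data capture, and ESR or CRP may pick up a delayed immune reaction.
- *The twelve-participant review will understate risk.* The text refers to safety data, not to safety endpoints, so it may include these events.
- *The share of time covered measures the loss.* Eight hours in a year is a tiny fraction of clock time, but acute reactions cluster after injection. Clock time is not risk.

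**Conclusion.** The point holds as a gap in the planned final safety analysis. After the first hour, embolization, symptomatic hypotension and desaturation not tied to new shunting have no safety endpoint. A clinical allergic or immune reaction has one only if ESR or CRP rises. No by-arm AE or SAE analysis is planned to fill the space. A report that follows the SAP could show no embolic endpoint although an embolization occurred hours or days after dosing.

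The size cannot be put as a number of missed events, because the documents give no rates or onset times. The conclusion rests on reading both lists as closed, which their wording supports, and on the absence of any final by-arm AE analysis in either document. It does not touch the primary efficacy analysis, and it does not imply that participants go unmonitored or that the DSMB is kept from late events.

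**What to change.** Amend SAP 5.4 and Protocol 11.9 as follows.

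1. Keep the 1-hour list unchanged as the acute subset.
2. Add two late safety endpoints over the existing 1- and 3-month windows, taken from AE and SAE records: pulmonary or systemic embolization, and allergic or other immune reaction judged possibly related to the product.
3. Plan a by-arm table of all AEs and SAEs for the final report, with symptomatic hypotension and clinically significant desaturation shown as named rows over the same windows.
4. Make the randomized comparison in Course 1, Arms 2 and 3 against Arm 1. Show Course 2 separately for each arm, and do not pool it as cells against placebo.
5. State that the twelve-participant review includes these events whatever their time of onset.

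The cost is wording and tables from data already collected; no visit, procedure or aspect of patient care changes. The downside is that some late events will be PAH background, particularly hypotension and desaturation, and a concurrent placebo comparison exists in Course 1 only. Keeping those two in the AE table, and not making them late endpoints, limits that noise.

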- Laboratory tests: sodium, potassium, chloride, TCO₂, blood sugar, BUN, creatinine, calcium, magnesium, phosphorus, alkaline phosphatase, total bilirubin, CPK, troponin, AST (SGOT), ALT (SGPT), LDH, gamma GT, albumin, uric acid, serum ferritin, CBC with differential, ESR, PT, PTT, INR (if warfarin sodium has been held for RHC procedure), brain natriuretic peptide (BNP), C-reactive protein (CRP)
- Additional blood samples will be taken for measurement of circulating biomarkers to be stored for no more than 15 years in the central biorepository at OHRI (no genetic testing will be performed)
- Urine collection for routine and microscopic analysis
- Urine pregnancy test for females with childbearing potential (to be done prior to administration of study product on the same day)

- **6MWD test (Baseline study)** and Borg dyspnea index (see Appendix D and E)
- Resting 12 lead ECG
- Pulmonary function testing (PFTs) [TLC, FVC, FEV₁/FVC, DLCO]
- 2D Echocardiogram with Doppler and saline contrast (as per Echocardiography Protocol)
- Quality of Life Questionnaire SF-36 (see Appendix G)
- Out-patient right heart catheterization for hemodynamic assessment (BP, HR, RAP, RVP, PAP, mPAP, PAWP, PVR, SVR, CO, CI, SvO2)
 - Patients who are currently receiving anticoagulant therapy (warfarin sodium, NOAC) will be managed according to the standard procedure at participating sites
 - Cardiac output will be determined using the thermodilution and/or Fick methods
- Cardiac MRI at sites where this is available (only for participants who are not on prostacyclin pumps and have no other exclusions for MRI such as claustrophobia) according to the Cardiac MRI Protocol.

Administration of study product:

- Insertion of a peripheral IV cannula (20 gauge or larger)
- Blood sample will be taken prior to study product delivery to assess levels of inflammatory markers, including IL-2, IL-6 and TNF, by multiplex cytokine array or other appropriate assay
- A total of 20 million cells (8 ml; concentration of 2.5 million cells per ml), or an equivalent volume of saline placebo, will be injected by hand injection at a rate of no more than 2 ml/minute in an outpatient clinic environment that is equipped for repeated assessments of BP, HR and oximetry as per the Study Product Delivery Protocol (Appendix H).

Post-treatment procedures:

- Monitoring of BP, HR, and oximetry every 15 minutes for at least one hour
- Adverse event monitoring and assessment

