#### **Exclusion Criteria:**

Patients will not be included in the study if ANY of the following exclusion criteria are present:

- Pregnant or lactating
- PAH related to any condition not covered under inclusion criteria, including but not limited to pulmonary venous hypertension, pulmonary veno-occlusive disease, pulmonary capillary hemangiomatosis, or chronic thromboembolic pulmonary hypertension
- Evidence of more than mild interstitial lung disease on Chest CT within the last 5 years (last 3 years for patients with scleroderma associated PAH)
- Treatment with an investigational drug, device or therapy within 3 months prior to the screening period or is scheduled to receive an investigational drug, device or therapy during the course of the study
- Any musculoskeletal disease or any other disease that would significantly limit ambulation
- Unrepaired or recently repaired (< 1 year) congenital systemic-to-pulmonary shunt other than patent foramen ovale
- Patients having three or more of the following four AMBITION study HFpEF risk factors will be excluded:

---

- BMI  $\geq 30 \text{ kg/m}^2$ ,
- History of essential hypertension,
- Diabetes mellitus (any type)
- Historical evidence of significant coronary artery disease (CAD) by ANY ONE of the following:
  - History of MI
  - History of PCI
  - Prior coronary angiography evidence of CAD (>50% stenosis in  $\geq 1$  vessel)
  - Previous positive Stress Test
  - Previous CABG
  - Stable angina
- Creatinine clearance  $<30 \text{ ml/min}$  (using the Cockcroft-Gault formula) or requires hemodialysis
- Inability to undergo the apheresis procedure due to poor venous access or laboratory tests that are not within acceptable ranges (not including INR for patients on Coumadin)
- Childs-Pugh class C liver cirrhosis
- Previous atrial septostomy
- Any other clinically significant illness or abnormal laboratory values (measured during the screening period) that, in the opinion of the Investigator, might put the subject at risk of harm during the study or might adversely affect the interpretation of the study data
- Anticipated survival less than 1 year due to concomitant disease
- History of cancer in the past 5 years (except for low grade and fully resolved non-melanoma skin cancer)

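### The late shunt safety endpoint counts only new shunting and names no reference echo, so it can miss worsening and blur attribution in Course 2

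*SAP*

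**What the plan says.** SAP 5.4 (Analysis of Safety) and Protocol 11.9 define the late shunt endpoint in the same words. It has two limbs.

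- **Grade limb:** "Evidence of new and more than mild right to left shunting (i.e. greater than grade 2 shunting", judged semi-quantitatively on agitated saline contrast echo.
- **Contrast limb:** "or new evidence of rapid appearance of contrast in the left atrium".

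The window is "Late (within 1 month [visits 0-2 and 6-8] or 3 months [visits 3 and 9] of study product delivery". Neither document names the echo against which *new* is judged. Neither says whether a mild shunt that later passes grade 2 is new, or what the top of the grading scale is.

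On entry, SAP 4.1 excludes "Unrepaired or recently repaired (< 1 year) congenital systemic-to-pulmonary shunt other than patent foramen ovale", so a patent foramen ovale is allowed. No eligibility criterion limits shunt grade. The first contrast echo, "2D Echocardiogram with Doppler and saline contrast (as per Echocardiography Protocol", is listed in Protocol 7.1 among the Month 0 procedures, which follow randomization and precede the first dose. It is repeated at Months 3, 6, 9 and 12 (Protocol 7.2 to 7.7; SAP 2.7). SAP 5.4 also lists "Right to Left shunting with rising right sided pressures" and intrapulmonary shunting among the events expected in this population.

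**The concern.** Some participants may already have a right-to-left shunt when dosing starts, and the plan's own list of expected events says such shunting occurs in PAH. A rule that counts only new findings does not register an increase in a shunt that is already there. Protocol 7.9 names pulmonary or systemic embolization as a possible immediate risk of the cells, so an increase in an existing right-to-left path is a change a safety reader would want to see.

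The design adds a second difficulty. Arm 1 moves from placebo to cells at Month 6, and Arm 3 receives a second course of cells. What counts as new in Course 2 then depends on a reference echo that the plan does not name. If it is chosen after the data are seen, the choice changes which events are reported and which treatment they are attached to.

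**Working it through.** The documents give no shunt rate and no figure for this endpoint, so there is nothing to reproduce. The check is which changes the wording counts.

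**1. Two readings of *new*.** Reading A: no shunt on the reference echo. Reading B: not already above grade 2 on the reference echo.

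**2. Changes counted by the grade limb.** The documents give only the cut (above grade 2). I assume a scale of 0–3 or 0–4 and list every upward change that ends above grade 2.

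| Assumed scale | Worsenings ending above grade 2 | Counted, reading A | Counted, reading B |
|---|---|---|---|
| 0–3 | 3 (0→3, 1→3, 2→3) | 1 (0→3) | 3 |
| 0–4 | 3 (to grade 3) + 4 (to grade 4) = 7 | 2 (0→3, 0→4) | 6 (3→4 missed) |

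Reading A misses 3 − 1 = 2 kinds of change on the shorter scale and 7 − 2 = 5 on the longer. Reading B misses 0 and 1. These are kinds of change, not shares of expected events.

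**3. Participants barred from the grade limb on both readings.** These are participants above grade 2 at Month 0, with *new* judged against Month 0. Their proportion *p* is not in the documents. As an assumption, for *p* from 5% to 30%:

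- expected number among 45 = 45*p*: 45 × 0.05 = 2.25 to 45 × 0.30 = 13.5
- chance of at least one among 45 = 1 − (1 − *p*)^45: 0.90 at 5%, 0.99 at 10%

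This shows only that such participants are plausible. It does not say how many would worsen. On a 0–3 scale none of them could rise a grade.

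**4. The contrast limb.** The limbs are alternatives. A participant with a Month 0 shunt but no rapid left-atrial contrast can still have the event through new rapid contrast. Only a participant who also shows rapid contrast at the reference echo is shut out of both limbs.

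**5. Course 2 (echoes at Months 9 and 12).** Assume no shunt at Month 0.

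| Case | *New* judged against Month 0 | *New* judged against Month 6 or the previous echo |
|---|---|---|
| Arm 1: shunt passes grade 2 on placebo in Course 1, then unchanged on cells | Can be counted within the window of cell delivery | Not counted |
| Arm 1 or 3: Course 1 shunt above grade 2 rises a further grade on cells (needs a scale beyond 3) | Counted, but looks the same as an unchanged shunt | Not counted by the grade limb |
| Arm 1 or 3: mild Course 1 shunt passes grade 2 on cells | Counted | Counted on reading B only |

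Neither reference works with the present wording. Month 0 can charge a placebo-period shunt to cells. A later reference loses worsening of a shunt already above grade 2, and on reading A worsening of a mild one too.

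**The case against.** The strongest reply has four parts.

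- **The natural reading is newly above grade 2.** Mild Month 0 shunts that progress would then count, and on a 0–3 scale no grade change would be missed. This stands as one possible reading, but the text does not choose it.
- **The scale and the meaning of *new* may be set in the Echocardiography Protocol,** which is cited but not supplied. That is possible. The counting rule for a safety endpoint should still be stated, or explicitly referenced, in the SAP.
- **Other capture exists.** All adverse events are recorded, the adverse event definition is broad, and embolization and a clinically significant saturation drop are separate early endpoints without the *new* condition. This stands as a partial backstop. It depends on an investigator calling an echo change an adverse event. Shunting is on the expected list, and expected serious events do not normally go to the research ethics board. The echo secondary outcome concerns right ventricular function, and I found no planned analysis of change in shunt grade.
- **No data are lost,** because the contrast echoes are serial. This stands, and it is why the remedy is cheap.

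A reader might go further and infer that everyone with a Month 0 shunt drops out of the endpoint, that a given share of events is missed, or that a between-arm comparison loses a given amount of power. The documents support none of these. The contrast limb stays open to many such participants. No baseline prevalence or worsening risk is given, and the plan specifies no between-arm test or denominator for this endpoint.

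**Conclusion.** The concern holds as a defect in the counting rule. Both limbs are limited to new findings and no reference echo is named, so the predefined endpoint can under-count worsening. The part that does not depend on the reading is that, judged against Month 0, a participant already above grade 2 cannot meet the grade limb, and one already showing rapid left-atrial contrast cannot meet the contrast limb. Whether a mild shunt that passes grade 2 is counted, and how Course 2 changes are attributed, depends on choices the plan leaves open. A shunt that first passes grade 2 in Course 1 from none at Month 0 is counted in Course 1; only its later worsening or attribution is in doubt.

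It would be too strong to say that harm is under-reported. The size of any under-count cannot be derived from these documents, and adverse event recording and the serial echoes remain. The counts of kinds of change rest on assumed scales of 0–3 and 0–4, and the participant numbers on an assumed 5–30% above grade 2 at Month 0. The change is still worth making before database lock, because it alters which safety events count.

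**What to change.** In SAP 5.4 and Protocol 11.9, replace *new and more than mild* with *new or worsened*, and define the event as either of:

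- a shunt above grade 2 that is of higher grade than on the participant's reference echo; or
- rapid left-atrial contrast that was absent on the reference echo.

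Name the reference: Month 0 for Course 1, and the pre-dose Month 6 echo for Course 2. State the grading scale or cite where it is defined.

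Add a table of shunt-grade shifts by arm and course, and report how many participants were already at the top grade on the reference echo and so could not worsen. A comparison of ordinal grade adjusted for Month 0 grade is optional.

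Under this rule the grade limb counts all 3 changes on the 0–3 scale and all 7 on the 0–4 scale. An unchanged placebo-period shunt in Arm 1 is no longer charged to cells, and worsening in Course 2 that ends above grade 2 is counted.

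The cost is wording and one table. Contrast echo is already scheduled at Months 0, 3, 6, 9 and 12, and the Month 6 echo is already a pre-treatment procedure. The downside is that some worsening from PAH progression will be counted. The concurrent placebo arm shows how much in Course 1. In Course 2 Arm 2 is on placebo, but after earlier cell exposure, so that comparison is less clean.
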